#### Detail: Refresh the Project on the Mobile App

It is recommended to click "Clean & Reset Mobile Project" to remove all data stored on the mobile device and replace with the most current project information from the main REDCap project.

#### What is "Send Emergency Data Dump"

When something prevents the app from sending data back to the server normally, you can use "Send Emergency Data Dump" option to send data to the server as a csv file. The file will show up under Mobile App File Archive tab.

	Cond Emerano av Date Duran
	Send Emergency Data Dump
data is so impo be parsed manu function proper	data to the server might rarely fail due to software limitations. Because the rtant, this alternate mechanism sends data to the server as a CSV that can ually. It should only be used in emergencies, and it requires the Internet to ly. The CSV file will show up under the REDCap Mobile App icon on the left- ind under the Mobile App File Archive tab.
	Proceed with Emergency Send

The **Visits Report** displays upcoming appointment dates based upon the birth date of the baby.

When the baby's date of birth is entered into the REDCap "Baby Data" form, the expected dates for upcoming events are populated into this report for easy "at a glance" viewing. The expected dates for upcoming appointments are based upon REDCap's "Days Offset" for each visit. The Study protocol's schedule of visits is determined at the Project setup, prior to collection of data.

#### Why do I care about this report?

• The Visits Report is used to display an expected (or rough draft) schedule of upcoming visits with the participant and to track the progress of completing these visits. It provides an "at a glance" look at each participant and tells what that person has completed, and when her next event is to be scheduled.

#### What does the report tell me?

• The Visits Report tells you what you need to do next. It can be used to coordinate scheduling of participants for upcoming events, by telling you what each participant's next event is, and when the study requires it to be accomplished.

#### How is the schedule determined?

• At the set-up of the Project, the BRIC Study Coordinator, in conjunction with the Principal Investigator, sets up a sequence of events for each participant in the study. This is based upon REDCap's "Days Offset" feature. For example: In this study, a 2-week postpartum visit is required. REDCap will set up to track 14 "Days Offset" from the baby's date of birth to schedule that visit. This projected date of visit will be displayed in this schedule.

#### What does "Days Offset" mean?

• "Days Offset" is the number of days before or after the "Index Event." These days are determined by the BRIC Study Coordinator, in conjunction with the Principal Investigator, and are used for scheduling activity and data collection schedules within the study.

#### What is an "Event"?

• An "Event" in REDCap means a specific visit or step in the study protocol.

#### What is an "Index Event"?

• The "Index Event" is a designated event, or field, that is the basis for calculating dates and schedules in REDCap. In this study, the "Index Event" is the baby's Date of Birth. All future events in REDCap are determined and calculated in relation to that fixed event.

#### What happens if I change the "Index Event"?

• Once data on a form are entered, and the form is saved in REDCap (by pushing the "Save" button on the bottom of the page), the Visits Report begins to calculate the schedule of events for that participant. If the specific "Index Event" (in this study it is the Baby's Date of Birth) is changed, e.g. a data entry error is discovered later, the entering of the corrected date will cause REDCap to recalculate and overwrite the expected visit dates and schedule. It is very important to enter the correct date (the "Index Event") properly the first time, so scheduling errors do not occur.

#### What forms do the data come from?

• The data can come from any of the Study forms. In the example of this study, the baby's date of birth is collected in the form titled "Baby Data." The completion date of scheduled events will come from the forms where that particular data is collected. The actual dates projected for the Visits Report are calculated behind-the-scenes by REDCap, based upon the days offset.

#### How do I make/request other reports?

• The BRIC Study Coordinator can assist in creating or updating reports. If the PI or Research Person(s) need to have access to creating reports, that can be arranged through the BRIC Study Coordinator.

#### I only see blank information. Why is that?

All data displayed in the Visits Report is triggered by the "Index Event" being entered into the proper form. In this study, if the "Baby's Date of Birth" is not entered there will be only blank data shown for that study participant. Similarly, the actual completion dates for the projected activities displayed in the report are filled in only after the data are entered into the appropriate forms. If the report fields are empty, that means the data have not been entered in the study forms.

#### Why do I only see the ID#, and not the name?

• For participant security, only the assigned ID# is shown. This helps control the privacy of participants. Authorized users may still access the participants' names as needed.

#### Why don't I see all of the participants?

• Only participants with a properly entered "Index Event" will show in the report. If a participant's data does not include this information, the report will not display that participant.

#### Why does it say I can't enter the information on a tablet? What do I do now?

• REDCap Mobile, the application used to run the data collection on tablets and mobile devices, is a great tool, but it is still being developed and improved. At this moment, data used as "Index Events" do not translate properly from mobile devices into the laptop/desktop application. As a result, if the "Index Event" – or other specified data – is entered on a mobile device/tablet, the reports will not function properly. Many institutions and entities are working to improve this issue. Currently, the "Index Event" must be entered via a laptop/desktop in order for the reports to function.

#### How do I run this report?

 On the left had side of the REDCap screen, you will find a section labeled "Reports." (This feature is currently only available on the laptop/desktop version of REDCap.) The Visits Report is listed there. The report is dynamic and will automatically update whenever it is selected. This report will always show the most current data available.

#### How do I use this report in Excel?

• Once you select the report to run, you will see a button labeled "Export Report." Clicking on this button will enable you to select the application you would like to export the data into. Excel, and many popular statistics software, is listed as an option. The export feature also allows important "de-identification" options.

#### How do I sort the report so I can use it easier?

• Reports will sort in the order chosen at report creation. If a different order is required, a new report should be created or the report should be exported and sorted through an external application.

# Kerver Randomization process Logistics (Ruised

#### **RANDOMIZATION PROCESS/LOGISTICS**

- 1. BRIC
   Prepare randomization table

   Packet ID# (sequential)/ group assignment (T or C)

   Randomization scheme: block randomization with random block size
- 2. BRIC Email randomization table to [name]/[name]'s supervisor, [name]. [[name] and her supervisor are-is unblinded.]
- 3. [name] Create packets

Insert appropriate material (T or C) based on the randomization table. Label with Packet ID# on outside of packet. Deliver packets (in numerical order) to Data Collectors (DCs)

4. DC Complete baseline data collection.

Retrieve next numbered packet. Use packets in sequential order. On Checklist Baseline Data Collection Phone Call FORM enter the Packet ID# for each Participant. Address the Packet with the Participant's mailing address.

Record on the paper log sheet for each Packet ready for mailing: PacketID#/Participant Initials/Date packet mailed

5. [name]?? View the Packet GroupAssnmnt REPORT on a daily basis. Open the Intervention FORM for each Participant listed in the report and enter the Group Assignment (T or C) for the given Packet ID#, by using the randomization table. Note: The report and form are blinded to all but [name] and Interventionists

6. Interventionist

View the Ready for Intervention Scheduling REPORT on a daily basis. Participants listed in the report are ready to be schedule for intervention visits. *Note: This report is blinded to all but [name] and Interventionists.*  Comment [JK1]: Does [name] also have access?

### Some as header

#### MAMA Bear Peer Counselors (MBPC) Protocol

#### Prenatal One-on-One Visit and phone contacts

Script for first visit:

 Thank you for taking time to meet with me today! Today I plan to talk with you about your goals for breastfeeding your baby, and share some resources that may be helpful to you in the future. We can also discuss any concerns you have regarding breastfeeding, or certain breastfeeding topics that you would like to learn more about.

#### • **To begin, I'd like to understand your views on breastfeeding.** *Ask one or more of the following, depending on individual needs:*

- Do you have other children?
  - If yes, ask: Have you breastfed before?
- What have you heard about breastfeeding?
- What are your goals for breastfeeding your baby?
- Do you have any concerns about breastfeeding?
- I think you might find the Coffective app helpful in supporting your breastfeeding goals. Have you heard about it? It's designed to help moms get off to a good start breastfeeding their babies, and to help them with concerns or problems if they should happen along the way. Show short intro video (1:24): https://vimeo.com/127838520. Show second video if time allows (5:41): https://vimeo.com/127839660
- Let's download the Coffective app to your phone and I will show you how to use it.
   If mother forgot her phone or you experience technical difficulties, refer to the Coffective website to show her the app features. Ask if she would like you to text her the link to where she can find it: http://www.coffective.com/ Make a plan for her to download the app when she gets home, and to discuss it at the next phone contact.
- Coffective also has a great checklist for helping you communicate your goals with your healthcare team when you deliver your baby. Sometimes you don't feel much like talking when you get to the hospital, so this checklist is helpful because you can simply hand it to the staff when you arrive. It can help them understand how to help you with your breastfeeding goals right after your baby is born. You can also share it with your significant other and/or your support persons. Having everyone "on the same page" is a great way to begin!
- During the completion of the Coffective checklist, address early postpartum topics applicable to mother, which are provided:
  - 1. Falling in love with your baby

- 2. Preparing for breastfeeding, benefits and expectations at hospital
- 3. Building your team
- 4. Benefits of exclusive breastfeeding
- 5. First hour after birth
- 6. Importance of rooming in
- 7. Breastfeeding positions
- 8. Protecting your milk
- 9. Feeding cues
- 10. Recommended duration (6 months) for exclusive breastfeeding

\*Remember not to provide medical advice, diagnose conditions, and to yield situations outside of your scope of practice. See "Scope of Practice for Peer Counselors" and "Yield List."

#### • Do you have any questions so far?

\*Remember not to provide medical advice, diagnose conditions, and to yield situations outside of your scope of practice. See "Scope of Practice for Peer Counselors" and "Yield List."

- After your baby is born, it can be challenging to take care of yourself. Planning ahead can help you and your baby stay healthy and have less stress during those first few weeks. Some of the things you can do now are:
  - Thinking about your short and long term goals
  - o Planning ahead for good nutrition despite being tired and busy
    - Example: preparing some frozen meals rich in lean proteins and vegetables.
  - Thinking of ways to get adequate rest
    - Example: sleeping when the baby sleeps
  - Enlisting the help of support persons
    - Example: listing three support persons and contact info in your booklet
    - Example: brainstorming ways in which your support persons could help you, such as grocery shopping, breastfeeding latch help, breastfeeding positioning help, laundry, or coming to hold the baby for a few hours while you sleep. Help with household chores and meals can allow you time to focus on rest and breastfeeding.

• Think about and set goals for weight management Ask the following questions as they apply:

- What do you feel your ideal weight is?
- What was your pre-pregnancy weight?
- What has your weight gain been during your pregnancy?
- Have you been able to be as active during pregnancy as you were before pregnancy?
- Has your doctor discussed his/her typical guidelines regarding resuming physical activity following birth?

- Do you have any concerns regarding weight management during or after pregnancy?
- Please write down any questions you might have. I'll be contacting you every 2 weeks by phone/text to see how you're doing.
  - After the visit, begin texting mother every 2 weeks to answer questions, provide additional education and support with breastfeeding and their healthy lifestyle goals
  - Any contact made with mother should be documented in RedCap System
- Once your baby is born, the postpartum home visit should be completed within 1-3 days after birth. Please contact me as soon as possible after your delivery so we can plan the visit. Make sure she has your accurate contact information handy.

#### Postpartum home visits and phone contacts

• Home visits should be completed within 1-3 days postpartum, and again at 6 weeks postpartum.

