## **Mama Bear Study Activities Timeline**

Funding is 4/1/16-3/31/18 (with extension through 3/31/19)

	Time	Location	Activities (Staff Responsible)	Incentive
1	~28 weeks	NCO Clinic	
 
Pre-screening (N)
 
Eligibility, consent, weight, blood, urine (DC) & (N if time permits)
 
	\$20
2	28-32 weeks	Phone	Baseline survey data collection (DC)	N/A
		Randon	nization into Intervention Group or Usual Care Group	
3	32-36 weeks	Home or NCO Clinic *	
 
Intro to program, breastfeeding support * (CHW)
 
	\$30
		NCO Clinic	• Usual Care group (DC) & (N if time permits)	φ30
4	Birth		
 
All participants receive a congratulations letter and a Baby Bear board book via mail ([name])
 
	N/A
5	1-3 days postpartum	Home *	
 
Breastfeeding support, self-care tips* (CHW)
 
	N/A
6	~6 weeks postpartum	NCO Clinic	
 
Weight & Survey (DC, CHW) & (N if time permits)
 
Intro to mobile app* (DC, CHW) & (N if time permits)
 
	\$50
7	~20 weeks Postpartum	Home	Data collection to include measured weight (DC)	\$50

Kev

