## **Clinic Visits**

~6-week post-partum data collection should occur at the clinic visit. This visit may occur for the participant anywhere between 2-8 wks post-partum.

After the participants' baby is born, contact the participant reminding them to schedule their post-partum visit at the clinic with the nurses. Ask the participant if the time scheduled would also be convenient for data-collection following the appointment. Document contact made within the "Contact log" on REDCap with details listed above. After the participants appointment has been scheduled, call participant 24hrs prior to their appointment providing them with a reminder of the appointment and that you will also meet with them during that visit.

If for some reason data collection cannot occur during the clinic visit, document the reason within the contact log and PLAN for completing visit. The next option for completing the visit would be over the phone and last option would be going to the participants home.

**Possible reasons may include:** No data collector available during clinic appointment, time was inconvenient for participant, or missed appointment.

[figure not shown]

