#### Visits

Before Visit

Before leaving office, identify the participant ID and download onto the mobile application. Before heading to the visit, be sure IPAD is completely charged.

• After Visit

Within **1 day** of completing visit, complete either the "Checklist Prenatal Home Visit" or "Checklist Early Post-Partum Home Visit" or "Checklist 6-week post-partum Home Visit" within the **web version** REDCap system. Click on the Participant ID, find specific Checklist (Prenatal, Early Post-partum, 6 week Post-partum), scroll to the bubble (displayed gray) and click to begin completing the form based on the previous visit. Once you have reached end of form, be sure to change status of form to "Complete" and save.

Lock this record for this form? If locked, no user will be able to edit this record on this form until someone with D bock Lock/Unlock privileges unlocks it.
.ock/Unlock privileges unlocks IL
Save Record
Save and Continue
Save and go to Next

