# MAMA BEAR Orientation Handbook for Peer Counselors

## Diet for a Healthy Breastfeeding Mom

raining CHW. 11.23.

Tips and suggestions for reference when working with Breastfeeding Mothers in MAMA Bear Study Presented by: [name] MS. CLS. PHP

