#### Analysis Plan:

**Aim 1: Feasibility of recruitment and retention:** Feasibility will be assessed at multiple points: enrollment rate (percent of eligible and approached women); percent of participants for whom study staff is notified of hospital admission for birth; percent of participants completing each additional data collection point. By compartmentalizing our feasibility assessment in this R21 exploratory/developmental project, we will be better able to target specific areas for refinement to inform our planned phase III trial. Retention will be assessed by the percent of participants who complete the 20 week postpartum data collection visit.

**Aim 2:** Acceptability will be measured at each data collection point using a brief questionnaire developed by the research team that will allow participants to rate the value and utility of the intervention content and give their opinions about the format, ease of use, and delivery method. Control group participants will be asked a similar set of questions to compare satisfaction with usual care practices. Engagement will be assessed as percent of intervention arm participants completing each planned intervention contact and by the frequency of log-ins to the online system, use of web/mobile-based tracking tools, and interactions with peer counselors. Feasibility and acceptability will be assessed separately from, but also in relation to the primary outcomes of breastfeeding duration and weight retention. For example, we will assess the number of women who discontinue BFing but continue tracking diet and exercise. These results will guide our structured interview questions planned for the final data collection visit (20 wks postpartum).

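### The Timeline lists the role that delivers the intervention as a collector of the 6-week weight and survey, contrary to the Data Collector Protocol, so 6-week self-reports and ratings may be biased in one arm

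*Combined protocol and SAP*

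**What the plan says.** **Study Activities Timeline.** Row 3 gives the CHW the prenatal contact, "Intro to program, breastfeeding support * (CHW", and row 5 gives the CHW the contact 1 to 3 days after birth, "Breastfeeding support, self-care tips". Row 6, the 6-week clinic contact, assigns weight and survey to the data collector (DC) and the CHW, with the nurse if time permits. It gives the same staff list for the next item, "Intro to mobile app* (DC, CHW". Row 7, the 20-week collection, lists the DC alone.

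**Peer Counselors Protocol, Postpartum home visits and phone contacts.** "Home visits should be completed within 1-3 days postpartum, and again at 6 weeks postpartum".

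**Data Collector Protocol.** The form table puts breastfeeding intensity, breastfeeding self-efficacy, the depression scale and repeated weight at about 6 weeks. The Clinic Visits section tells the data collector to arrange and carry out this collection at the clinic, then by phone, and at the participant's home as a last resort. One reason it gives for not collecting at the clinic is "No data collector available during clinic appointment".

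**Interventionist Protocol, Visits.** The interventionist completes a form called "Checklist 6-week post-partum Home Visit". The data collector's form table has an almost identically named checklist.

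**Analysis Plan, Aim 2.** "Acceptability will be measured at each data collection point using a brief questionnaire".

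**The concern.** The person who has encouraged a woman to breastfeed, and who delivers the programme, is listed as one of those who may ask her at 6 weeks how feeding is going and what she thinks of the programme. Women tend to answer such questions favourably when the asker has a stake in the answer. Usual-care women have no counsellor, so the error would differ between arms, and randomisation does not remove it.

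The stated objective of this pilot is to estimate effect sizes, and its feasibility findings are to inform a planned phase III trial. A bias of this kind would carry into that planning and would not shrink with more women. Weight read from a scale is little exposed. The self-reports and the ratings are.

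**Working it through.** **1. Is the CHW the peer counsellor?** The abbreviation key is not in the text reviewed, so this is an inference. The CHW's contacts in rows 3 and 5 of the Timeline are the visits scripted in the Peer Counselors Protocol. The CHW training slides also follow the heading "MAMA BEAR Orientation Handbook for Peer Counselors". The inference is reasonable.

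**2. Who collects at 6 weeks?**

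| Source | Collector at about 6 weeks |
|---|---|
| Timeline, row 6 | DC and CHW; nurse if time permits |
| Clinic Visits | Data collector; phone, then home, as fallback; CHW not mentioned |
| Interventionist Protocol | Visit checklist, interaction log, baby data; no survey form or weight |
| Peer Counselors Protocol | Counselling visit; no survey step |

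Only row 6 names the CHW for the survey. No section bars the CHW from administering it, and none says that the acceptability rating is self-completed. Row 6 and Clinic Visits therefore need to be reconciled.

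**3. What is exposed?** The 6-week intensity, self-efficacy and depression reports are exposed. So are the acceptability ratings, if the Aim 2 schedule is followed; that questionnaire does not appear in the form table.

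**4. What is not shown to be exposed?** The randomised comparison in Aim 3 is at 20 weeks, and the DC alone collects then. The Analysis Plan does not say which visit supplies the weaning date. For the secondary comparison it mentions 6-week electronic records for non-enrolled patients, without saying that enrolled women's values come from this survey.

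**5. The plan's own figure.** The plan states 80% power for 0.65 SD with 80 women, two-sided alpha 0.05. The allocation ratio is not stated; I assume 40 per arm.

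- Noncentrality = 0.65 × √(40/2) = 2.91, which gives t-test power of 0.819.
- The stated figure is reproduced, and this point does not change it.

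**6. Scale only; every input below is an assumption.** Let s be the share of intervention women surveyed by their counsellor.

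- *Any 6-week self-report, no true effect.* An arm-wide shift of 0.1, 0.2 or 0.3 SD would give a significant t-test in about 7%, 14% or 26% of trials with 40 per arm, against a nominal 5%.
- *Acceptability on a 5-point item.* Shift = s × over-rating. With over-rating of 0.25 to 0.5 points, s = 0.5 gives 0.5 × 0.25 = 0.125 to 0.5 × 0.5 = 0.25 points.
- *Weaning day, only if taken from the 6-week survey.* Shift = s × (share weaned by then) × (days over-stated). With 30–60% weaned and 3–14 days over-stated:
  - s = 1 gives 0.30 × 3 = 0.9 to 0.60 × 14 = 8.4 days
  - s = 0.5 gives 0.45 to 4.2 days
  - at an SD of 40–50 days, these are 0.9/50 = 0.02 to 8.4/40 = 0.21 SD, and 0.45/50 = 0.01 to 4.2/40 = 0.11 SD

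**The case against.** The case rests on one staff list in a summary table. Row 6 gives the same list to the survey and to the app introduction, so it may only record who is present. The operational sections keep the roles apart. Clinic Visits treats the absence of a data collector as a reason for the collection not to happen at the clinic, which suggests that the CHW is not a substitute. The two checklists record that a visit took place and are not outcome instruments, so their similar names prove little. The counsellor's 6-week visit is described as a home visit and the collection as a clinic contact, so they may be separate occasions.

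Most of this stands. It makes shared collection possible rather than established. It does not remove the conflict, because staff working from the Timeline could properly have the CHW administer the survey.

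A reader might infer more in three ways, none of which the documents support:

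- *That the main outcomes are biased.* The 20-week collection is by the DC alone, and neither the weaning date nor the enrolled women's values in the secondary comparison are tied to the 6-week survey.
- *That the counsellor surveys usual-care women, because the survey line has no asterisk.* This depends on a table key that is not in the text reviewed.
- *That the bias can be put at several days of breastfeeding.* The upper figures need every intervention woman to be surveyed by her counsellor, and all inputs are assumed.

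**Conclusion.** The point holds as a conflict between the Timeline and the Data Collector Protocol over who collects 6-week data. If row 6 is followed, a differential reporting bias is possible in the 6-week self-reports and the acceptability ratings. Its direction would tend to favour the intervention; its size is unknown, and the ranges above only show scale. The conclusion assumes that the CHW is the peer counsellor and that some CHWs would in fact administer the forms. It does not extend to the 20-week weight, and it extends to breastfeeding duration only under a data source that the plan does not specify. Severity is minor to moderate: the remedy is cheap and the exposure avoidable, but the trial's main comparison is not shown to be compromised.

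**What to change.** 1. In Timeline row 6, remove the CHW from the weight-and-survey item. That leaves the DC, or the nurse if time permits, in both arms, and agrees with Clinic Visits.
2. In Clinic Visits, state that the survey and any acceptability rating are completed before any counselling or app introduction at the same contact, without the counsellor present. State also that the existing phone or home fallback is used if no data collector is free.
3. In Timeline row 6, leave the app introduction to the CHW, who is already listed for it. The DC, who also collects the 20-week outcomes, then does not deliver programme content or learn the allocation from doing so. The Randomization Process section already restricts the group-assignment form and report to one named role and the interventionists. This step closes one route only: row 3 lists the DC for the usual-care contact, and ratings of intervention content also reveal the arm.

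The cost is a few lines of text and no new staff. The downside is that a few 6-week surveys will move to the fallback when no data collector is at the clinic.
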